10.9 Communication and Reporting Serious Adverse Events (SAEs)

Any grade 4-5 adverse event (CTCAE v4.0) deemed by the MSM and/or the DSMB to be temporally associated with the treatment will prompt cessation and trigger the stopping rules. Triggering the stopping rules will prompt notification of the FDA and IRB. If a patient that receives study treatment dies, and the DSMB determines that it may be related to the treatment, then the study will be terminated and a comprehensive safety review undertaken.

10.9.1 Timeline for Reporting SAE's

- 1. The PI will notify the MSM and DSMB of any communication from the FDA concerning the trial within 72 hours of notification.
- MSM and DSMB written reports regarding SAEs will be submitted to the IRB within five working days.
- Subject deaths will be reported to the MSM and IRB by telephone within 24 hours of discovery, and entered into IRB electronic database (iRIS) within five working days.
- SAE's directly related to the cellular infusion will be reported to the MSM and IRB within five days of discovery and entered into the IRB electronic database (iRIS).
- 5. Other AEs do not need to be reported if the PI determines the AE is expected or due to the natural progression of the subject's underlying disease, however an internal log/record will be kept of these for tracking potential risks and reporting purposes.

11. HUMAN SUBJECTS

11.1 Institutional Review Board (IRB) Review and Informed Consent

This protocol and the informed consent document and any subsequent modifications will be reviewed and approved by the University of Texas Health Science Center at Houston Committee for the Protection of Human Subjects (CPHS), also known as the IRB. A signed consent form will be obtained from the parent(s) or Legally Authorized Representative (LAR) after a thorough explanation of the purpose of the study, the study procedures (including the bone marrow harvest/sham procedure, infusion, MRI, and assessment procedures), follow-up visits, potential risks/benefits, the time commitment involved, and measures to protect confidentiality. Adequate time will be given for questions. A copy of the signed consent form will be given to the parent(s)/LAR. In addition, a written note will be placed in the patient's medical chart documenting the communication between investigator and the parent(s)/LAR about the research.

11.2 Subject Confidentiality

To protect against loss of confidentiality, subjects' names will be replaced by a study identification number on case report forms, reports and on computer entry into the database. No identifying information will be mentioned in any presentations or publications. Strict security will be maintained, with limited access only to the password protected database, and all personnel involved will be trained to be aware of the importance of maintaining privacy. Clinical information will not be released without written permission of the subject (or parent(s)/LAR), except as necessary for monitoring by the DSMB, IRB, FDA, or other State or Federal regulatory agencies.

11.3 Study Modification/Discontinuation

The study may be modified or discontinued at any time by the DSMB, IRB, the OHRP, the FDA, or other government agencies as part of their duties to ensure that research subjects are protected.

12. PUBLICATION OF RESEARCH FINDINGS

Publication of the results of this trial will be governed by the policies and procedures developed by the Executive Committee. Any presentation, abstract or manuscript will make available for review by the sponsor prior to submission.

IRB NUMBER: HSC-MS-12-0876
UTHealth
The University of Texas

14. APPENDIX A

Bone Marrow Group:

												1
Study Procedures	Screening Period	Baseline Clinic Visit	Admission to MHH	Study Day 1 (Post-Infusion)	Study Day 2-21 (Post-Infusion)	* 6-Month Follow-Up Clinic Visit	* 1-Year Follow-Up Clinic Visit	* 1-Year Crossover Group Clinic Visit	Crossover Group Admission to MHH	Crossover Group Study Day 1 (Post-Infusion)	Crossover Group Study Days 2 - 21 (Post-Infusion)	* 2-Year End of Study Clinic Visit
Review of Medical Records	Х	х						х				
Consent		¹ X	9 3					Х				
Randomization		х									2	
History	Х	х				х	Х	Х				х
Physical		х	X	х		х	Х	Х	х	Х		х
Videotaped Motor/Cognitive Evaluation		х				х	х	х				х
Vital Signs		х	X	х	х	х	Х	Х	х	Х	Х	х
Infectious Disease Tests			² X									
Lab Evaluation		³ X	3X	3X	⁴ x	³ X	³ X	³ X	³ X	³ X	⁴ x	³ X
Chest X-Ray			х	х		х	Х		х	х		х
DT-MRI			Х				Х		Х		5	х
Bone Marrow / Sham Harvest			Х						⁶ x			
Stem Cell or Placebo Infusion			х						⁶ X			
Neuropsych Evaluation		х				×	x	x				х
Hospital Discharge				⁵ X						⁵ x		
Post-Infusion Safety Monitoring					х						х	
Evaluation for AE/SAEs		х	x	х	х	х	×	X	х	x	x	x

^{*} The 6 month return visit window is +/- 14 days from infusion and +/- 21 days for the 1 and 2 year return visits.

¹ The informed consent document will be sent to the family/LAR during the screening period and reviewed by conference call before the baseline visit.

². Infectious Disease Tests include HIV, Hepatitis, Syphilis, and West Nile Virus.

³ Lab tests include CBC with Differential and Platelets, and Comprehensive Metabolic/Coagulation Panels.

⁴ Post-infusion CBC and basic chemistry pannel on day 21 (+/- 7 days).

⁵ Subjects will receive 24 hours of monitoring post-infusion before discharge.

⁶. Placebo Crossover to BMMNC harvest and stem cell infusion.

Cord Blood Group:

Study Procedures	Screening Period	6 - 8 Weeks Before Visit	Baseline Clinic Visit	Admission to MHH	Study Day 1 (Post-Infusion)	Study Days 2 - 21 (Post-Infusion)	• 6-Month Follow-Up Clinic Visit	+ 1-Year Follow-Up Clinic Visit	* 1-Year Crossover Group Clinic Visit	Crossover Group Admission to MHH	Crossover Group Study Day 1 (Post-Infusion)	Crossover Group Study Days 2 - 21 (Post-Infusion)	* 2-Year End of Study Clinic Visit
Review of Medical Recods	х												
Consent			¹ x					Х	x				x
History			Х										8
Physical			х	Х	Х		Х	Х	Х	Х	Х		х
Infectious Disease and HLA Tests		²x							х				
CBR Release of Cord Blood Tests		³ X							х				
Randomization	1	⁴ x		6. F.									8
Shipment of Cord Blood		⁵ X											
Videotaped Motor/Cognitive Evaluation			×				х	x	x				х
Vital Signs			Х	Х	Х	X	Х	Х	X	X	X	X	Х
Lab Evaluation			6X	⁶ x	⁶ х	⁷ x	⁶ X	⁶ х	⁶ х	⁶ X	⁶ X	⁷ X	⁶ X
Chest X-ray				X	X		х	Х		X	X		х
DT-MRI	.			Х		8	9	Х		X			X
Stem Cell or Placebo Infusion				x						⁸ x			
Neuropsych Evaluation			х				х	x	x				х
Hospital Discharge					⁹ x						⁹ x		
Post-Infusion Safety Monitoring						x						x	
Evaluate for AE/SAEs			х	х	х	х	х	х	х	х	х	х	х

- * The 6 month return visit window is +/- 14 days from infusion and +/- 21 days for the 1 and 2 year return visits.
- 1 The informed consent document will be sent to the family/LAR during the screening period and reviewed by conference call before the baseline visit.
- ² Subject will have HLA & basic infectious disease tests prior to baseline visit. Maternal infectious disease tests will also be required if not avialable from CBR.
- ³ After the signed informed consent document is received, CBR will be contacted to release cord blood information (HLA Type, Cell Count, Contaminates).
- ⁴ Cord blood subjects will be randomized after comfirmation of viable cord blood stem cells, confirmation of HLA match, and neg. infectious disease test results.
- ⁵ CBR will ship the frozen hUCB to the GSCL 7 to 14 days before the visit. Umbilical cord blood for subjects assigned to the placebo group will not be released from CBR until the 1 year cross-over visit.
- ⁶ Lab tests include CBC with differential and platelets, comprehensive metabolic and coagulation panels, and hepatic function tests.
- ⁷ Post-infusion CBC and basic chemistry pannel on day 21 (+/- 7 days).
- ⁸ Cross-Over Group Stem Cell infusion.
- ⁹ Subjects will receive 24 hours of monitoring post-infusion before discharge.

15. Appendix B: Table of Psychological and Functional Outcome Tests

Age	Motor	Adaptive Behavior	Visual-Spatial Processing	Learning	Language
2-2.5	GMFM-88	VABS2			
2.6-3	GMFM-88	VABS2			PPVT4/EVT2
3	GMFM-88	VABS2		NEPSY-II	PPVT4/EVT2
4	GMFM-88	VABS2	MVPT-3	NEPSY-II	PPVT4/EVT2
5	GMFM-88	VABS2	MVPT-3	NEPSY-II	PPVT4/EVT2
6	GMFM-88	VABS2	MVPT-3	NEPSY-II	PPVT4/EVT2
7	GMFM-88	VABS2	MVPT-3	NEPSY-II	PPVT4/EVT2
8	GMFM-88	VABS2	MVPT-3	NEPSY-II	PPVT4/EVT2
9	GMFM-88	VABS2	MVPT-3	NEPSY-II	PPVT4/EVT2
10	GMFM-88	VABS2	MVPT-3	NEPSY-II	PPVT4/EVT2

16. Appendix C: DSMB CHARTER

DATA AND SAFETY MONITORING BOARD CHARTER

Protocol Title:	Autologous Cell Therapies for Cerebral Palsy-Chronic (ACT for CP)				
Principal Investigators:	[name], [name]				
Co-Investigator:	[name], [name], [name], [name], [name]				
Study Staff:	[name], MSN, RN, [name], MSN, RN, CCRC				
Protocol Number:	HSC-MS-12-0876				
BB IND Number:					
Sponsor:	CBR, Inc., TIRR Foundation, Let's Cure CP Foundation				
Document Version Date:	18 OCT 2017				

Purpose:

The purpose of this charter is to define the responsibilities of this Data and Safety Monitoring Board (DSMB), its membership, and timing of meetings. It will also provide the procedures used to carry out these responsibilities.

DSMB Responsibilities:

The DSMB has the following responsibilities:

- Review and sign this charter signifying understanding of responsibilities;
- Review the research protocol, informed consent documents and plans for data safety and monitoring;
- Evaluate the progress of the trial, including periodic assessments of data quality and timeliness, participant recruitment, accrual and retention, participant risk versus benefit, performance of the trial site, and other factors that can affect study outcome;
- Consider factors external to the study when relevant information becomes available, such as scientific or therapeutic developments that may have an impact on the safety of the participants or the ethics of the trial;
- Make recommendations to the PI about continuation, termination, or other modifications of the trial based on the observed beneficial or adverse effects of the treatment under study;
- If appropriate, conduct interim analysis of efficacy in accordance with stopping criteria which are clearly defined in advance of data analysis and have the approval of the DSMB;
- Ensure the confidentiality of the trial data and the results of monitoring; and,
- Recommend solutions to address problems with study conduct, enrollment, and sample size and/or data collection.

Membership:

The DSMB will consist of at least three four-members. Three members will constitute a quorum. All members must be completely independent of the trial and have no financial, scientific, or other conflict of interest with the trial. Collaborators or associates of [name], and [name], are not eligible to serve on the DSMB. The DSMB includes

IRB NUMBER: HSC-MS-12-0876
UTHealth
The University of Texas

experts in or representatives of the fields of relevant clinical expertise, clinical trial methodology, and biostatistics.

DSMB members will be provided a full copy of the protocol along with pertinent documents prior to the first meeting. Documents may be provided via secure email or in hard copy. Hard copies of any documents are considered confidential, and will be mailed via intra-office mail or certified carrier. Updated or new documents will be distributed by the DSMB coordinator.

Scheduled Reports:

The study team should provide reports at least a week prior to the date of the meeting. The study team must submit subject summary reports to the DSMB Chair and Medical Safety Monitor within 30 days of each completed baseline visit, and thereafter, prior to each DSMB meeting, or as requested by the DSMB..

DSMB Report Format:

DSMB reports will include the following:

- Accrual/Recruitment Information include number of patients screened, enrolled, completed, withdrawn and reasons for withdrawals if any. For multi-site studies include distribution by site.
- 2. Characteristics of Subjects Enrolled include gender, ethnicity (Hispanic/ Non-Hispanic), race: White, Black/African American, etc.
- 3. Study information table with age, gender, missed doses, extra doses if any, PTT, whether hypertensive or not, NIH stoke scale before and after intervention.
- 4. Adverse events include description, grade, expectedness, relatedness.
- 5. Compliance with protocol include protocol deviations.
- 6. Any other information as requested by the DSMB or Study P.I.

Safety Reports:

- 1. Serious Adverse Events (SAE) that are determined by the PI to be unexpected + related will be submitted to the DSMB within 7 calendar days of the determination by telephone or fax; Submit written report no later than 15 calendar days of the determination.
- 2. All other SAEs will be collected and submitted with the standard DSMB reports as described above.

Meetings:

The first meeting will be held at trial initiation and after the 5th subject has completed the baseline infusion visit. Subsequent meetings will be held after every 6 months, or as needed, at the discretion of the Chair to address safety concerns.

IRB NUMBER: HSC-MS-12-0876
UTHealth IRB APPROVAL DATE: 10/23/2017
The University of Texas

Meetings may be in person or via teleconference, depending upon the schedule of the members. If members of the DSMB cannot attend a scheduled meeting, the members present *may* decide the meeting will be cancelled and rescheduled to reconvene at the earliest possible time.

The Principal Investigator and research team will be notified of planned meetings no less than three weeks prior to the meeting date. The Principal Investigator will be expected to submit the required reports at least two weeks before to the scheduled meeting.

The Principal Investigator and/or study team members will attend regularly scheduled open DSMB meetings to provide specific clarification or respond to issues. The DSMB may invite guests to meetings for their expertise or for needed information. Discussion will focus on the conduct and progress of the study with special attention to the aggregate safety and efficacy data. The Principal Investigator may present summary statements of previously submitted updates, adverse events, etc. Review and discussion of unblinded primary outcome data will be limited to voting DSMB members during closed session meetings, or at the discretion of the DSMB Chair.

Recommendations:

Following a DSMB review, the board must submit a written report to the PI. The options available for the outcome of the review are:

- 1. Recommend continuation with no modification,
- 2. Recommend continuation with modification(s) to protocol,
- 3. Recommend suspension of enrollment pending additional information,
- 4. Recommend suspension of all trial activities pending additional information,
- 5. Recommend termination of trial.

Recommendations to the Principal Investigator must have majority approval by the Board members. Prior to dissemination, the Chair will review summary statements and recommendations from DSMB members.

Distribution of DSMB Report:

The DSMB Chair will formalize the recommendations in secure email or formal letter and forward to the DSMB Coordinator for forwarding to the PI. The DSMB coordinator should forward the DSMB's final recommendations to the Principal Investigator within 2 weeks of the meeting. The Principal Investigator is responsible for dissemination to the study team, IRB, FDA, and any other entity.

Confidentiality:

All materials, discussions and proceedings of the DSMB are completely confidential. Members and other participants in DSMB meetings are expected to maintain confidentiality.

DSMB Member Acknowledgement:

DSMB members will confirm their understanding of the DSMB Charter, roles, responsibilities and disclosure of conflict of interests by e-mail acknowledgement.

IRB NUMBER: HSC-MS-12-0876
UTHealth
The University of Texas

17. Appendix D: Maternal Infectious Disease Testing

FDA 21 CFR part 1271 requires donor eligibility determination, based on donor screening and testing for relevant communicable diseases and disease agents, for all human cells, tissues and cellular & tissue-based products (HCT/P) collected on or after May, 2005. However, 21 CFR part 1271.90 allows exceptions to this requisite and also elaborates on the labeling requirements for these special cases. The relevant exception to this protocol states that "You are not required to make a donor eligibility determination under 1271.50 or to perform donor screening or testing under 1271.75, 1271.80 and 1271.85 for: (1) Cells and tissues for autologous use".

Nevertheless, we have chosen to perform maternal infectious disease markers (IDM) testing in this protocol. The maternal IDM results (if available) will be released to the research team along with the cord blood sterility and cell count information after informed consent and permission for releasing the test results have been obtained from the parent(s). The IDM tests include: Human Immunodeficiency Virus (HIV) type 1, HIV type 2, Hepatitis B virus, Hepatitis C virus, Human T-cell lymphotrophic virus (HTLV) type 1, HTLV type 2, and Syphilis.

Again, donor eligibility will not be determined for autologous infusions but specific labeling rules will be applied. The subject will be excluded from the study if any IDM result is positive or reactive EXCEPT for the following cases:

- Donor is CMV positive. Since CMV infection is not a relevant communicable disease or disease agent, the product will not be excluded but will require specific labeling.
- If donor mother screens HBcAb reactive and HBsAq non-reactive, the product will not be excluded but will require specific labeling.
- For syphilis, if donor tests reactive on a NON-treponemal screening and non-reactive on a specific treponemal confirmatory test, the product will not be excluded but will require specific labeling.

Per CBR, less than 10% of cord blood collections do not have maternal IDM testing performed. In the event that a subject meets criteria for study entry, but CBR does not have the maternal IDM results, the parent(s) will be able to submit IDM results that were performed during the hospital admission for delivery. If the IDM tests were not completed during the pregnancy, the mother will be required to have IDM testing completed at her expense and the correspondent lab results submitted to the PI.

Whenever applicable, HCT/P must be prominently labeled per 21 CFR 1271.90 as follows:

Label Type	Usage
"FOR AUTOLOGOUS USE ONLY"	On all autologous products
"Warning: Advise Patient of Communicable Disease Risk"	If the result of any screening or testing performed indicate the presence of relevant communicable disease agent. For example, medical and/or family history puts donor at high risk for acquiring communicable disease agent.
"Warning: Reactive test results for (name of disease agent or disease)"	If the result of any screening or testing performed is positive or reactive
"Advise recipient that screening and testing of the donor is not performed at the time of cryopreservation of the cells or tissues but have been performed subsequently"	Screening or testing not performed at the time of cryopreservation but at later time

☐ Refer to the Chemistry and Manufacturing Section of the IND for more detailed information. ACT for CP Protocol V18

The University of Texas

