5.1.7 Post-Infusion Period

The day following infusion will be considered Post-Infusion Day 1, regardless of what time of the day the infusion was given. Post-infusion monitoring will include hemodynamics, infusion related toxicities (pulmonary, hepatic, and renal lab indices),

and neurologic complications. Laboratory tests will include a CBC with differential, chemistry panel, hepatic function panel, and coagulation panel. As part of the pulmonary monitoring a chest x-ray will be performed and blood-oxygen saturation will be monitored by finger oximeter. In the event of pulmonary dysfunction, standard supportive therapy will be given. The research team will review the first 24 hours of post-infusion monitoring for AE/SAE's and determine if the subject is eligible for discharge home. Any serious adverse event as described in the Statistical Considerations section will be reported immediately and referred to the DSMB and evaluated for potential relationship to the protocol.

Prior to discharge, the parent(s)/LAR will be given detailed instructions regarding signs and symptoms of infection such as fever, malaise, and chills and told to check the subject's body temperature twice daily for three weeks after discharge (through postinfusion day 21). Parents(s)/LAR will be instructed to immediately report neurological changes or seizure activity to the research team. A CBC and basic chemistry panel will be obtained 21 days post-infusion (+/- 7 days). Parent(s)/LAR will be given the option of having the lab tests performed by their PCP or, for local families, here at UTHealth. The research team will have daily contact with the parent(s)/LAR through post-infusion day 21. Monitoring information will be recorded on the case report form and any reports of abnormalities will be relayed to the study PI/Co PI immediately. If indicated, the parent(s)/LAR will be instructed to have the subject seen be their PCP for further evaluation. Local families may opt to be seen by the research team for adverse events evaluation.

After discharge, the subject's PCP will be given discharge summary information. The PCP will be asked to consult with the study PI on any AE/SAE's post-infusion to ensure that appropriate therapy/treatment is given to the subject.

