10.4 Medical Safety Monitor (MSM)

[name] will serve as the MSM. [name] is faculty for the Department of Hematology/Oncology-Bone Marrow Transplantation at The Methodist Hospital and the Center for Cell and Gene Therapy in Houston, Texas. [name] is experienced in the field of cellular therapies, including bone marrow harvest and transplantation. In addition, he is experienced in the release criteria of cellular products and potential AEs related to infusion toxicity. He has served on previous DSMBs, including having served as the DSMB Chair of the Phase 1 Pediatric TBI stem cell trial. [name] primary responsibility will be to review SAEs in real time to ensure good clinical practice and to quickly identify safety concerns. He may suggest protocol modifications to prevent the occurrence of particular adverse events. He will remain blinded to the treatment assignment, unless the DSMB approves unblinding, and will review SAE reports following post-infusion Day 21 of each subject (if applicable) for submission to the PI,

DSMB, FDA and IRB, and prior to each DSMB meeting. [name] is not affiliated with UT Health in any manner, nor does he practice within the Memorial Hermann Hospital System. The MSM will work in conjunction with the IMM and the DSMB to ensure the safety of the intervention in this trial.

All reports of hospitalization due to infection or neurological events, and all subject deaths will be reported to the MSM.

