10.6 Adverse Experience Reporting

10.6.1 Overview

All safety data will be reviewed by the Medical Safety Monitor (MSM) in real time, as well as, the Independent Medical Monitor (IMM) at regular monitoring visits according to the monitoring plan. Based on the data, the MSM may suggest protocol modifications to prevent the occurrence of particular adverse events. The data will also be reviewed by the DSMB at bi-annual meetings, or on an as-needed basis if required. The DSMB can recommend protocol modifications and/or study termination because of safety findings. All FDA, OHRP and the University of Texas Health Science Center at Houston IRB requirements for reporting adverse experiences will be followed.

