10.8.1 Stopping Rules

- 1. ANY death that is deemed by the DSMB to be related or possibly related to the study treatment.
- 2. Both P:F ratio < 70 AND PaC02 > 90 within the first 48 hours post BM infusion occurring in a single subject.
- 3. AST/ALT > 900 U/dl in the first 24 hours post infusion occurring in a single subject.
- 4. Grade 4 5 CNS cerebrovascular ischemia event or Grade 4 5 seizure event as defined in the NCI CTCAE v4.0 occurring within 12 hours of BMMNCs or Cord blood Cell re-infusion.
- 5. Any Grade 4 5 Adverse Event as defined in the NCI CTCAE v4.0 and determined to be temporally-related by the Medical Safety Monitor and/or DSMB.

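### SAE timelines to the DSMB conflict, and under the charter a death that stopping rule 1 asks the DSMB to judge may wait for the routine report

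*Combined protocol and SAP*

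**What the plan says.** Three places set a route for SAEs, and they differ.

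- **Sections 5.1.7 and 5.2.9 (Post-Infusion Period, both arms):** "Any serious adverse event as described in the Statistical Considerations section will be reported immediately and referred to the DSMB".
- **Appendix C, DSMB Charter, Safety Reports:** the expedited route covers SAEs "determined by the PI to be unexpected + related will be submitted to the DSMB within 7 calendar days of the determination", with a written report by 15 days. For the remainder: "All other SAEs will be collected and submitted with the standard DSMB reports as described above".
- **Section 10.9.1:** "Subject deaths will be reported to the MSM and IRB by telephone within 24 hours of discovery". SAEs directly related to the infusion go to the same two recipients within five days. The DSMB appears in neither line.

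On meetings, the charter says "Subsequent meetings will be held after every 6 months, or as needed, at the discretion of the Chair to address safety concerns", and section 10.6.1 agrees: "The data will also be reviewed by the DSMB at bi-annual meetings, or on an as-needed basis if required".

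Two provisions depend on the board's own opinion. Stopping rule 1 (section 10.8.1) is any "death that is deemed by the DSMB to be related or possibly related to the study treatment". Section 10.9 ends the study if the DSMB finds that a treated patient's death may be related to the treatment. The PI makes the attribution that is recorded for each event (section 10.7.2).

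**The concern.** A site cannot tell from these texts when the DSMB must learn of a given SAE. For most SAEs that is an untidy instruction. For deaths it touches a stopping rule. Rule 1 acts only on the DSMB's judgement, yet under the charter the PI's view of expectedness and relatedness decides whether the death reaches the board in days or with the next routine report. The attribution that the board is meant to check therefore controls how soon it can check it. An as-needed meeting helps only once the chair knows that there is something to discuss.

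**Working it through.** No sample size, power or event count is involved, so the plan has no figure to reproduce. The check is a side-by-side reading.

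**Step 1. Is a death an SAE?** Yes. Section 10.6.2.4 lists death among the outcomes that make an event serious, so every general SAE route also covers deaths.

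**Step 2. Routes and clocks.**

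| Source | Events | Recipient | Clock |
|---|---|---|---|
| 5.1.7, 5.2.9 | Any SAE | DSMB, by referral | Reported immediately; no separate clock for the referral |
| Charter, Safety Reports | SAEs the PI calls unexpected and related | DSMB | 7 calendar days from the PI's determination; written by 15 |
| Charter, Safety Reports | All other SAEs | DSMB | With the standard report |
| 10.9.1 | Deaths | MSM, IRB | 24 hours from discovery |
| 10.9.1 | SAEs directly related to the infusion | MSM, IRB | Five days from discovery |
| 10.4 | Deaths; hospitalizations for infection or neurological events | MSM | None stated |

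Section 10.9.1 also expects MSM and DSMB written reports on SAEs to reach the IRB within five working days. That assumes the DSMB has already been told, although no line in that section tells it.

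**Step 3. Longest wait under the charter.** Meetings are half-yearly: 365.25 / 2 = 182.6, about 183 days. This bound applies once the regular cycle has begun; the charter ties the meeting before that cycle to the fifth subject's baseline infusion visit. It also assumes that no ad hoc meeting is called and that nobody passes the event on sooner.

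**Step 4. What decides between 7 days and the routine report?** Only the PI's judgement, on both conditions. The 7 days run from that judgement and not from discovery, and the charter sets no limit on reaching it. Section 10.6.2.5 ends by equating unexpected with not previously observed. Read literally, a second related event of the same kind would drop to the routine report.

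**Step 5. Which deaths are covered by another rule?** Grade 5 is death (section 10.7.1). Rule 5 covers Grade 4-5 events found temporally related by the MSM and/or the DSMB, and section 10.9 says that such a finding stops treatment and triggers the stopping rules. So the MSM alone can act on a temporally related death. The term has no general window: section 6.2.5 attaches 12 hours to it, for neurologic changes only. Follow-up runs 2 years and long-term safety is part of the primary objective (section 1.1), so a later death may be left to rule 1.

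**Step 6. Will the SAE routes be used at all?** Section 3 names a 10 to 15% SAE incidence as what the study could detect; it is not a forecast. If the true rate were in that range, P(at least one SAE) = 1 - (1 - p)^n.

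- n = 30: 1 - 0.90^30 = 0.958; 1 - 0.85^30 = 0.992.
- n = 20 first randomized to cells (30 x 2/3): 1 - 0.90^20 = 0.878; 1 - 0.85^20 = 0.961.

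This concerns SAEs in general and says nothing about how likely a death is.

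**The case against.** The strongest reply is that the board is not cut off. A reader might infer that deaths bypass the DSMB. The documents do not support that. A death is an SAE and so falls under sections 5.1.7 and 5.2.9 and under one of the two charter routes. The MSM's review of SAE reports (section 10.4) is also for submission to the DSMB, among others. What is true is narrower: the 24-hour death notice does not name the DSMB.

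A reader might also infer that the death rule cannot work. That too goes beyond the text. All deaths go to the MSM without a filter on PI attribution, rule 5 lets the MSM trigger the stopping rules alone for a temporally related death, section 8.3 allows MSM review to lead to suspended enrolment, and ad hoc meetings are provided for. Rule 1 may be delayed; it is not disabled.

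Other safeguards exist but are partial. The independent medical monitor alerts the DSMB to an unexpected or unduly high SAE rate (section 10.3), which one death need not be. The charter's subject summary reaches the chair within 30 days of each completed baseline visit, but its content is not specified and it would miss later events.

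Sections 5.1.7 and 5.2.9 can be read more narrowly than a demand for instant DSMB notice: they describe the post-infusion period, and the word immediately governs the reporting, with the referral left untimed. Part of the conflict may therefore be one of scope. That reading still leaves the referral without a clock.

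Finally, a reader might see a contradiction in section 10.4, which describes SAE review in real time and also says that the MSM "will review SAE reports following post-infusion Day 21 of each subject". These can be two separate tasks, and no finding rests on them.

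**Conclusion.** The concern holds as an internal inconsistency with a consequence for one stopping rule. The SAE timelines to the DSMB differ between sections 5.1.7/5.2.9, section 10.9.1 and the charter. Following the charter and section 10.9.1 as written, a death that the PI does not call both unexpected and related may reach the DSMB only with the routine report, up to about 6 months later, although rule 1 and section 10.9 need the board's own judgement. That is a worst case: it assumes that the charter prevails over sections 5.1.7 and 5.2.9, that the MSM does not pass the death on, and that no ad hoc meeting is called. With rule 5 and the MSM in place, the remaining gap is mainly later deaths that are not judged temporally related.

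The number of children enrolled during such a wait cannot be taken from the documents, which give no accrual period. On an assumed 2 to 4 years it would be 30/4 = 7.5 down to 30/8 = 3.75 per half-year. That is illustrative, and the conclusion does not depend on it. The point should be corrected because it is cheap to correct and bears on a safety rule in a trial whose primary objective is safety.

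**What to change.** Reconcile sections 5.1.7, 5.2.9, 10.4, 10.9 and 10.9.1 and the charter's Safety Reports into one table that gives recipient, clock and starting point (discovery or determination) for each event class, and have the other sections refer to it. In that table, send deaths, and any event whose stopping rule needs a DSMB judgement, to the DSMB chair at the same time as the MSM, whatever the PI's attribution.

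The route for the remaining SAEs must be reconciled too. The sponsor has to choose it, and this point does not favour the immediate or the routine version. While editing, correct the cross-reference in sections 5.1.7 and 5.2.9, which looks to the Statistical Considerations for a description of SAEs that stands in section 10.6.2.4.

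The cost is wording changes in the protocol and charter, and a few extra notifications. No sample size, analysis or clinical rule changes.
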